2.3.2 KNOWN POTENTIAL BENEFITS

There is no direct benefit to individual subjects or to the group of participants in the study

2.3.3 ASSESSMENT OF POTENTIAL RISKS AND BENEFITS

This trial can eventually lead to porcine xenografts becoming the standard of care when it comes to wound healing.

3 OBJECTIVES AND ENDPOINTS

OBJECTIVES	ENDPOINTS	JUSTIFICATION FOR ENDPOINTS
Primary		
To compare overall scar quality and aesthetic outcome following second intention healing or porcine xenograft dressing of surgical wounds on the lower extremities.	1. POSAS observer scale total score. The primary outcome will be the total score of the POSAS observer scale, assessed at the 3-month follow-up visit by two blinded evaluators who will not be involved in the placement of the porcine xenograft. For each patient, scores from the two blinded investigators will be combined by calculating the mean. The POSAS (Patient and Observer Scar Assessment Scale) is a validated assessment tool used for the	To determine whether porcine xenografts improve wound healing.

NIH-FDA Clinical Trial Protocol Template - v1.0 7 Apr 2017 Northwell Version: 9/16/2019

OBJECTIVES	ENDPOINTS	JUSTIFICATION FOR ENDPOINTS
	assessment of all types of scars by professionals and patients [17-19]. The observer scale is comprised of 6 items (vascularity, pigmentation, thickness, relief, pliability, and surface area) scored on a scale from 1("like normal skin") to 10 ("worst scar imaginable"). The total score is calculated as the sum of the six items (range, 6-60). All patients will be evaluated by two blinded observers, who will be selected from the other attending physicians and/or resident physicians at the site. However, all patients will not be evaluated by the same set of observers due to differences in physician schedules. Agreement between the blinded evaluators will be assessed using the intraclass correlation coefficient (ICC). The form of the ICC will be the ICC (1,2).	
Secondary		
To compare patients' assessment of scar quality, healing time, scar size, and pain level following second intention healing or porcine xenograft dressing of surgical wounds on the lower extremities.	1. POSAS patient scale total score. Study participants will complete the POSAS patient scale at the 3-month follow-up visit. The POSAS patient scale consists of 6 items assessing patients' subjective opinion of scar quality in terms of pain, itching, color, pliability, thickness, and relief. Each item is scored from 1 (normal pigmentation, no itching, etc.) to 10 ("worst imaginable scar or sensation"). The total score of the POSAS patient scale is calculated as the sum of the six items (range, 6- 60).	To determine whether porcine xenografts improve wound healing.

OBJECTIVES	ENDPOINTS	JUSTIFICATION FOR ENDPOINTS
	2. Healing time. Healing time will be measured in weeks based on patient's responses to question 1 of the weekly follow-up questionnaire ("Is the wound completely healed (i.e., wound is completely closed with no open areas)?"). For example, a patient who first replies "Yes" to this question on the third weekly follow- up questionnaire will be assigned a healing time of 3 weeks. A more objective measure of healing time would not be feasible given our resources and patient schedule.	
	3. Ratio of scare size to initial defect size. The initial postoperative defect size will be measured by the investigator prior to intervention in terms of length and width using a sterile ruler. Initial defect area will be calculated as length times width. Scar size will be measured in terms of length and width at the 3-month follow-up visit, and scar area will be calculated as length times width. The outcome will be calculated by dividing the scar area by the initial defect area.	
	4. Pain score at 1 week following surgery. Patients' pain scores will be measured based on their response to question 2 of the weekly follow-up questionnaire. Patients will be asked to rate their current pain level at the operative site on a scale from 1 (no pain) to 10 (worst imaginable pain).	
	5. Number of weeks with pain score above 1. Patients' pain scores will be measured based on their response to question 2 of the weekly follow-up questionnaire. Patients will be asked	

OBJECTIVES	ENDPOINTS	JUSTIFICATION FOR ENDPOINTS
Tertiary/Exploratory/Safety	to rate their current pain level at the operative site on a scale from 1 (no pain) to 10 (worst imaginable pain). The POSAS observer scale, POSAS patient scale, healing time, and number of weeks with pain score above 1 are all subjective endpoints. The ratio of scar size to initial defect size and complication rates are objective endpoints.	
To compare complication rates following second intention healing or porcine xenograft dressing of surgical wounds on the lower extremities.	 Infection. Patient's charts will be reviewed at the completion of their 3-month office visit follow-up in order to analyze if they visited the dermatologist between the date of surgery and 3-month office visit and if infection was diagnosed. Bleeding. During each of the weekly follow-up questionnaires and during the 3-month follow-up visit, patients will be asked if they have experienced any post-operative bleeding that led to a visit to the 	To help keep the patients as safe as possible.
	physician (yes/no) and if there was any intervention performed by the physician to stop the bleeding (yes/no). The number and percentage of patients who experienced bleeding at any time during the 3-month follow-up period will be reported.	

OBJECTIVES	ENDPOINTS	JUSTIFICATION FOR ENDPOINTS
	3. Pain. The proportion of patients	
	with a pain score > 6 at the operative	
	site will be assessed at one week	
	following surgery. This will be based	
	on the patient's response to the	
	weekly follow-up questionnaire, with	
	scores ranging from 1 (no pain) to 10	
	(worst imaginable pain).	

4 STUDY DESIGN

4.1 OVERALL DESIGN

The authors will conduct a comparative two-arm study investigating outcomes of second intention healing versus porcine xenograft placement of post-operative Mohs surgery or excision wound defects. This will be a randomized evaluator blinded study with a prior power analysis. Basic demographic data will be obtained including date of birth, sex, and race. Medical record number will be retained to obtain phone number or address for patient call back should patient not show for their follow-up appointments.

Surgical defects 8 mm in diameter or larger on the lower extremities will be eligible for enrollment. Only patients with one wound will be eligible for enrollment. Primary intention (also known as linear layered) repair is not feasible in many patients with defects on the foot, ankle, or distal extremity as these are sites under high tension and poor circulation. Patients with small post-op defects many also opt not to be sutured via primary intention to avoid physical activity restrictions due to the increased risk of wound dehiscence. When closed via primary intention, a 0.8cm defect results in a scar of greater than or equal to 2.4cm.

Patients will be randomly assigned in a 1:1 ratio to receive either a porcine xenograft or to allow the wound to granulate via second intention. If primary/linear repair is not an acceptable option, the standard of care at Northwell is to allow the wound to heal on its own via second intention post-operatively. Due to recently published retrospective studies, there is a suggestion that porcine xenografts may be a feasible alternative to second intent healing. Currently, it is the surgeon's (and patient's) choice, after a discussion of risks and benefits of each modality, what is done.

A randomization schedule will be generated by the Biostatistics Unit at the Feinstein Institute for Medical Research to assign a repair method (porcine xenograft placement or second intention healing).

Block randomization will be used to ensure balance in the number of patients allocated to each treatment group. The randomization schedule will be uploaded to REDCap by a statistician outside of the study team. The PI, who will screen eligible subjects, will not have user rights for the Randomization Setup module within REDCap, and will thus be blinded to which treatment arm is next on the randomization list. Due to the nature of the treatment, it will not be possible to blind the patients. Patients will be asked not to inform the blinded physician observers which treatment they received. The PI will use the "Randomize" button within REDCap to assign patients to porcine xenograft or second intention healing after they have been consented and enrolled in the study.

Prior to intervention the defect size will be measured in terms of length and width using a sterile ruler.

After procedure completion wound care instruction will include daily dressing changes and application of petroleum jelly using a cotton tipped applicator to the wound daily until it is healed.

Weekly questionnaires will be given to the patients by phone or email follow-up. All complications and adverse events would be monitored and recorded for both study groups. Assessment of the scar will be blinded in nature.

The mode of treatment for participants will remain consistent throughout the 3-month period, as both methods are reliable for this type of defect. It is not general practice to place a xenograft on a wound healing by second intention or to remove a xenograft after one has been placed to switch to second intention. Should there be any complications, a modified intention to treat principle, described in Section 9, will be adhered to.

The scars for both study groups will be measured at a single follow up visit after 3 months \pm 1 month, and two blinded investigators will then assess the scar for the primary efficacy endpoint at this time. The blinded evaluators will be other MDs not involved in the study who are working in the dermatology department. The Principle Investigator will speak with the physician to outline what needs to be recorded for each patient. The validated physician observer scar assessment instrument (POSAS) will be used for this purpose. Scar size will consist of a length x width measurement using a ruler.

The research team consists of one physician who will perform all of the surgical procedures, which will remove bias in technique. The study statistician will be blinded to the treatment groups in order to avoid bias or the appearance of bias. The statistician will keep the information on which treatment is "A" and which treatment is "B".

4.2 SCIENTIFIC RATIONALE FOR STUDY DESIGN

To compare overall scar quality, aesthetic outcome, healing time, scar size, pain level, and complication rates following second intention healing or porcine xenograft dressing of surgical wounds on the lower extremities.

4.3 JUSTIFICATION FOR DOSE

This is a device study not a drug trial.

4.4 END OF STUDY DEFINITION

A participant is considered to have completed the study if he or she has completed all phases of the study including the last visit or the last scheduled procedure shown in the Schedule of Activities (SoA), Section 1.3.

The end of the study is defined as completion of the last visit or procedure shown in the SoA in the trial globally.

5 STUDY POPULATION

- Over 18 years of age
- Able to give informed consent themselves
- Willing to return for follow-up visits
- Post-operative defects greater than 8 mm (in greatest diameter or length of circular or oval geometric shape) on the lower extremities (including the feet)
- Single defect

5.1 EXCLUSION CRITERIA

- Mentally handicapped
- Unable to understand written and oral English
- Incarceration
- Under 18 years of age
- Unwilling to return for follow-up
- Pregnant women
- Wounds less than 8 mm in length
- Wounds on the head, neck or digits
- Patients in which primary linear closure is recommended

5.2 LIFESTYLE CONSIDERATIONS

During this study, participants will discuss with the physician any limitations of activities based on the treatment provided, as is done with the normal protocol.

5.3 SCREEN FAILURES

Patients will either qualify to receive the device or don't.

5.4 STRATEGIES FOR RECRUITMENT AND RETENTION

Patients scheduled for cutaneous surgery at the Northwell Health Dermatology Clinics at Lake Success and Bay Shore will be approached by the research staff to see if they are interested in participating in the study. A pre-operative surgical consultation for lower extremity cutaneous malignancies is not standard of care. As such, many dermatologic surgery patients receive same-day consult and surgery. Thus it is, in the majority of cases, not feasible to obtain consent prior to the day of surgery. It would pose a burden on the patient and surgeon and may result in delay of surgical care to require a preoperative surgical consultation prior to treatment of lower extremity cutaneous malignancies.

Patients will not be encouraged nor coerced in any way. We do not plan to advertise this study, as the patient population in the department will produce sufficient opportunities to identify patients. Subjects are not compensated for participation in this study.

6 STUDY INTERVENTION

6.1 STUDY INTERVENTION(S) ADMINISTRATION

6.1.1 STUDY INTERVENTION DESCRIPTION

Only patients with one wound will be eligible for enrollment. Primary intention (also known as linear layered) repair is not feasible in many patients with defects on the foot, ankle, or distal extremity as these are sites under high tension and poor circulation. Patients with small post-op defects many also opt not to be sutured via primary intention to avoid physical activity restrictions due to the increased risk of wound dehiscence. When closed via primary intention, a 0.8cm defect results in a scar of greater than or equal to 2.4cm.

Patients will be randomized to either receive a porcine xenograft or allow the wound to granulate via second intention. If primary/linear repair is not an acceptable option, the standard of care at Northwell is to allow the wound to heal on its own via second intention post-operatively. Due to recently published retrospective studies, there is a suggestion that porcine xenografts may be a feasible alternative to second intent healing. Currently, it is the surgeon's (and patient's) choice, after a discussion of risks and benefits of each modality, what is done.

Prior to intervention the defect size will be measured in terms of length and width using a sterile ruler.

After procedure completion wound care instruction will include daily dressing changes and application of petroleum jelly using a cotton tipped applicator to the wound daily until it is healed.

6.1.2 DOSING AND ADMINISTRATION

There will be no dosing since patients will either be randomized to receive the porcine xenograft or continue with second intent healing.

6.2 PREPARATION/HANDLING/STORAGE/ACCOUNTABILITY

6.2.1 ACQUISITION AND ACCOUNTABILITY

Normal porcine xenograft procedures that the dermatology practice follows.

6.2.2 FORMULATION, APPEARANCE, PACKAGING, AND LABELING

Normal porcine xenograft procedures that the dermatology practice follows.

6.2.3 PRODUCT STORAGE AND STABILITY

Normal porcine xenograft procedures that the dermatology practice follows.

6.2.4 PREPARATION

Normal porcine xenograft procedures that the dermatology practice follows.

6.3 MEASURES TO MINIMIZE BIAS: RANDOMIZATION AND BLINDING

A randomization schedule will be generated by the Biostatistics Unit at the Feinstein Institute for Medical Research to assign a repair method (porcine xenograft placement or second intention healing). Block randomization will be used to ensure balance in the number of patients allocated to each treatment group. The allocation ratio will be 1:1. The randomization schedule will be uploaded to REDCap by a statistician outside of the study team. The PI, who will screen eligible subjects, will not have user rights for the Randomization Setup module within REDCap, and will thus be blinded to which treatment arm is next on the randomization list. The PI will use the "Randomize" button within REDCap to assign patients to porcine xenograft or second intention healing as they are enrolled.

There will be one physician who will perform all of the surgical procedures, which will remove bias in technique. There will additionally be two blinded physicians who will be tasked with observing the scar and assessing the primary efficacy endpoint (POSAS observer scale total score). The study statistician will be blinded to the treatment groups in order to avoid bias or the appearance of bias. All data provided to the statistician will list the treatment group as "A" or "B".

6.4 STUDY INTERVENTION COMPLIANCE

Porcine xenograft placement and second intention healing are methods of healing that are currently used and is the patient's and physician's choice. Administration of either porcine xenograft or second intention is part of the standard of care and will be completed as such. An initial visit form will be completed to log the method of treatment administered and will be reviewed to ensure that the randomized treatment was completed.

6.5 CONCOMITANT THERAPY

For this protocol no prescription medication will be utilized as this is a device study.

6.5.1 RESCUE MEDICINE

The study sites will supply the topical application of rescue medication that will be obtained locally. The following rescue medications may be used:

Silver Nitrate Wood Applicator Sticks Henry Schein Model: 1126994

The use of rescue medication is allowable after the formation of hypergranulation tissue which may begin to occur 6-8 weeks post-operatively, but typically the use of rescue medications should be delayed, if possible, for at least 10-12 weeks following the surgical date. This is considered standard of care, as it allows the patient the chance to heal without adjunct medication. The date and time of rescue medication administration as well as the name and regimen of the rescue medication will be recorded in RedCAP. Follow-up after the application of the rescue medication will occur every 6 weeks or until healed, per our surgical standard of care.

For patients receiving rescue medication, the POSAS observer scale total score (primary outcome), POSAS patient scale total score (secondary outcome), and ratio of scar size to initial defect size (secondary outcome) will be recorded at the patient's follow-up visit within 6 weeks of administering the rescue medication, or at a subsequent follow-up visit when the wound is fully healed. (Note that it is not possible to administer the POSAS instrument, a scar assessment tool, if the wound is not completely healed).

As described in Section 9.3, a modified intention-to-treat analysis will be used, in which all patients who have been assessed for the primary study endpoint will be analyzed according to their randomized treatment group.

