8 STUDY ASSESSMENTS AND PROCEDURES

8.1 EFFICACY ASSESSMENTS

The authors will conduct a comparative two-arm study investigating outcomes of second intention healing versus porcine xenograft placement of post-operative Mohs surgery or excision wound defects.

This will be a randomized evaluator blinded study with a prior power analysis. Basic demographic data will be obtained including date of birth, sex, and race. Medical record number will be retained to obtain phone number or address for patient call back should patient not show for their follow-up appointments.

Surgical defects 8 mm in diameter or larger on the lower extremities will be eligible for enrollment. Only patients with one wound will be eligible for enrollment. Primary intention (also known as linear layered) repair is not feasible in many patients with defects on the foot, ankle, or distal extremity as these are sites under high tension and poor circulation. Patients with small post-op defects many also opt not to be sutured via primary intention to avoid physical activity restrictions due to the increased risk of wound dehiscence. When closed via primary intention, a 0.8cm defect results in a scar of greater than or equal to 2.4cm.

Patients will be randomized to either receive a porcine xenograft or allow the wound to granulate via second intention. If primary/linear repair is not an acceptable option, the standard of care at Northwell is to allow the wound to heal on its own via second intention post-operatively. Due to recently published retrospective studies, there is a suggestion that porcine xenografts may be a feasible alternative to second intent healing. Currently, it is the surgeon's (and patient's) choice, after a discussion of risks and benefits of each modality, what is done.

Prior to intervention the defect size will be measured in terms of length and width using a sterile ruler.

After procedure completion wound care instruction will include daily dressing changes and application of petroleum jelly using a cotton tipped applicator to the wound daily until it is healed.

Weekly questionnaires will be given to the patients by phone or email follow-up until 12 weeks postsurgery.

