9.3 POPULATIONS FOR ANALYSES

A modified intention to treat analysis will be performed. All patients will be analyzed according to randomized treatment assignment, unless a patient prefers an alternative treatment method between the time he/she is randomized and the procedure (in which case the patient will be excluded from the study). The **Modified Intention-to-Treat (mITT) Population** will consist of all patients who receive the study intervention and show up for the 3-month office visit follow-up, during which the primary endpoint is evaluated. The Modified Intention-to Treat Population will also include patients who required the rescue therapy, and had the primary endpoint assessed at a follow-up visit when the wound had completely healed. This population will be used to analyze the primary endpoint and all secondary endpoints.

The **Safety Population** will consist of all patients who receive the randomized study intervention. This population will be used to analyze all safety endpoints.

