9.4.3 ANALYSIS OF THE SECONDARY ENDPOINT(S)

Analysis of all secondary endpoints will be considered exploratory. Thus, the analysis of secondary endpoints is not dependent on findings of the primary endpoint, and no adjustments for multiplicity will be made.

1. **POSAS patient scale total score.** Study participants will complete the POSAS patient scale at the 3month follow-up visit. The POSAS patient scale consists of 6 items assessing patients' subjective opinion of scar quality in terms of pain, itching, color, pliability, thickness, and relief. Each item is scored from 1 (normal pigmentation, no itching, etc.) to 10 ("worst imaginable scar or sensation"). The total score of the POSAS patient scale is calculated as the sum of the six items (range, 6-60).

2. **Healing time.** Healing time will be measured in weeks based on patient's responses to question 1 of the weekly follow-up questionnaire ("Is the wound completely healed (i.e., wound is completely closed with no open areas)?"). For example, a patient who first replies "Yes" to this question on the third weekly follow-up questionnaire will be assigned a healing time of 3 weeks. A more objective measure of healing time would not be feasible given our resources and patient schedule.

3. **Ratio of scare size to initial defect size**. The initial postoperative defect size will be measured by the investigator prior to intervention in terms of length and width using a sterile ruler. Initial defect area will be calculated as length times width. Scar size will be measured in terms of length and width at the 3-month follow-up visit, and scar area will be calculated as length times width. The outcome will be calculated by dividing the scar area by the initial defect area.

4. **Pain score at 1 week following surgery.** Patients' pain scores will be measured based on their response to question 2 of the weekly follow-up questionnaire. Patients will be asked to rate their current pain level at the operative site on a scale from 1 (no pain) to 10 (worst imaginable pain).

5. **Number of weeks with pain score above 1.** Patients' pain scores will be measured based on their response to question 2 of the weekly follow-up questionnaire. Patients will be asked to rate their current pain level at the operative site on a scale from 1 (no pain) to 10 (worst imaginable pain).

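### Healing time has no defined value for a wound still open at week 12, rescued or not, so the rank test as written leaves out the slowest healers

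*Combined protocol and SAP*

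**What the plan says.** - **Definition (9.4.3, endpoint 2).** Healing time is the week of the first Yes to question 1 of the weekly questionnaire. The only rule is an example: a patient whose first Yes is on the third questionnaire "will be assigned a healing time of 3 weeks". Nothing covers a patient who never answers Yes.
- **End of observation (8.1).** "Weekly questionnaires will be given to the patients by phone or email follow-up until 12 weeks postsurgery". The largest value that can be recorded is therefore 12.
- **Rescue (6.5.1).** Silver nitrate is allowed once hypergranulation forms, but "typically the use of rescue medications should be delayed, if possible, for at least 10-12 weeks following the surgical date". After that, "Follow-up after the application of the rescue medication will occur every 6 weeks or until healed, per our surgical standard of care".
- **Later recording (6.5.1).** For rescued patients, both POSAS totals and the scar ratio are taken at the "follow-up visit within 6 weeks of administering the rescue medication, or at a subsequent follow-up visit when the wound is fully healed". Healing time is not on this list.
- **Population (9.3).** The mITT population "will also include patients who required the rescue therapy", provided that the primary endpoint was assessed once the wound had closed. "This population will be used to analyze the primary endpoint and all secondary endpoints".
- **Analysis (9.4.3).** Each secondary endpoint gets a Mann-Whitney test, a Hodges-Lehmann estimate with 95% interval, mean (SD) and median (IQR). No censoring, worst-rank, cap or missing-value rule is given. All secondary analyses are declared exploratory.

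**The concern.** The definition and the analysis population do not fit together. Section 9.3 counts rescued patients in the healing-time analysis once they have healed, while 9.4.3 can give a number only to wounds reported closed by week 12. The field stays blank for a wound open at that point, and a rank test run on the recorded values skips blanks. Whether a value is missing then depends on the outcome itself: the patients who heal most slowly go, and more of them go from the slower arm. Faster healing with xenograft is one of the hypotheses in section 2.2, so a true benefit would be understated and harder to detect.

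The gap sits in 9.4.3 and applies to any wound open at week 12. Rescue is simply the route by which the plan expects to meet such wounds.

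**Working it through.** **Timeline.** The last questionnaire is at week 12. A patient rescued at week 10 has two questionnaires left (weeks 11 and 12); one rescued at week 12 has none. A six-week interval puts the next check no later than week 10 + 6 = 16 to week 12 + 6 = 18. An earlier check is possible, since 6.5.1 speaks of a visit within six weeks and the ordinary visit is at 3 months ± 1 month. Neither visit feeds healing time. A rescued wound reported closed by week 12 has a value; one still open has none.

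**Plan's own figure, for the arm size.** Section 9.2: n per arm = 2(1.96 + 0.842)² × 6.5²/6² = 18.4, so 19, or 38 in total. 38/0.864 = 43.98, so 44 evaluable, 22 per arm. 44/0.9 = 48.9, so 50 recruited. This reproduces and is not in dispute.

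**Effect of the missing rule.** The documents give no healing-time distribution, so the following inputs are assumptions: lognormal times with log-SD 0.35, rounded up to the next weekly questionnaire; 22 per arm; two-sided Mann-Whitney test at .05 with tie correction; 4000 runs (Monte Carlo SE at most 0.8 points). The chance of being open after week 12 is 1 − Φ(ln(12/median)/0.35). For a median of 9: ln(12/9) = 0.288, 0.288/0.35 = 0.82, giving about 20.5%. Expected open wounds = 22 × (sum of the two proportions).

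| Medians, xenograft v second intention (weeks) | Open at week 12 | Expected open of 44 | Power, dropped | Power, ranked last | Loss (points) | Mean Hodges-Lehmann, dropped v coded 13 (weeks) |
|---|---|---|---|---|---|---|
| 5 v 6.5 | 0.6% v 4.0% | 1.0 | 58.5% | 64.0% | 5.5 | −1.34 v −1.46 |
| 6 v 8 | 2.4% v 12.4% | 3.3 | 58.4% | 71.6% | 13.2 | −1.52 v −1.92 |
| 7 v 9 | 6.2% v 20.5% | 5.9 | 38.2% | 59.2% | 21.0 | −1.26 v −1.81 |
| 7 v 9, rescue closes half of those open at week 10 by week 12 | 3.1% v 10.3% | 2.9 | 50.9% | 60.1% | 9.2 | −1.52 v −1.78 |
| 8 v 10 | 12.4% v 30.3% | 9.4 | 27.0% | 51.3% | 24.3 | −1.03 v −1.65 |

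With medians 4 v 5.5 (0.1% v 1.3% open, 22 × 0.014 = 0.3 wounds), power is 80% dropped and 81% ranked last.

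**Benefit only in the tail.** If healers are equally fast (median 7, log-SD 0.30) but 4% v 20% stay open, rejection is 4.6% dropped and 13.9% ranked last; the mean Hodges-Lehmann difference is 0.00 v −0.69 weeks.

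**False positives.** With no true difference (medians 8 v 8, 12.3% open in each arm), rejection is 4.5% dropped, 4.4% coded 12 and 4.4% ranked last. Taking the best of the three after seeing results gives 7.0%.

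**Choice of code.** Coding open wounds 12 instead of 13 changes power by at most 2 points. What matters is whether they are kept.

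**Other model.** Weibull times (shape 2.5, hazard ratio 2.0, second-intention medians 7, 8.5 and 10) leave 7%, 19% and 34% open with second intention and 0.4%, 4% and 11% with xenograft. Power dropped v ranked last is 36% v 47%, 22% v 49% and 12% v 45%. The direction is the same; the losses (11, 27 and 33 points) are larger at similar open fractions.

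**The case against.** The plan never says to drop these patients. Section 9.3 puts rescued, later-healed patients in the population for every secondary endpoint, which points towards keeping them. Once they are kept, codes 12 and 13 give nearly the same power. On that view only a numeric code is missing, and most statisticians would choose a tied worst rank. The endpoint is exploratory and patient-reported, and the trial was not sized on it. The rationale for the amendment expects healing within 12 weeks and few rescues. The issue is also ordinary end-of-observation handling, not a fault in the timing of rescue.

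Much of this stands. The mITT wording does favour keeping these patients, and few open wounds means little loss. It does not close the gap: inclusion in the population supplies no number, the stated definition yields none, and software omits blanks by default. Dropping, coding 12, ranking last or using the week of the healed visit are all open until someone chooses.

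The documents do not settle one further point. The end of 6.5.1 describes the mITT population as patients assessed for the primary endpoint, which requires a closed wound, while the first mITT sentence in 9.3 could admit a patient who attends at 3 months with an open one. The simulation analyses every open wound, so if some never enter the mITT population it overstates what a rule recovers.

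A reader might also infer that rescue distorts the primary comparison, or that analysing rescued patients as randomized is wrong. The documents do not support this: 6.5.1 and 9.3 make POSAS assessable at a healed visit and keep patients in their randomized arm.

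**Conclusion.** The point holds for any wound open at week 12, rescued or not. As written, 9.4.3 gives these patients no healing time, and a Mann-Whitney test on the recorded values omits them and pulls a true difference towards zero.

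Under the lognormal assumption the cost is about 1 to 5 power points when about one wound in 44 or fewer is open, which fits the protocol's expectation, and about 13 to 21 points when 12% to 21% of the slower arm is open. The Weibull check shows that the size depends on the assumed shape, so the figures are indicative.

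A reader might infer from the larger rows that a heavy loss is likely. The documents give neither a healing-time distribution nor a rescue rate, and they expect few rescues. Nor is there a threat to the main result: the primary endpoint is untouched, and no single rule raises the false-positive rate. The change should be made because it is cheap and must precede sight of the data; it is not critical.

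**What to change.** Keep the Mann-Whitney test, the mITT population and analysis as randomized. Add to 9.4.3, endpoint 2:

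> A wound not reported healed by the week-12 questionnaire, and known to be open then or later, is ranked last (tied) in the Mann-Whitney test and coded 13 weeks for the Hodges-Lehmann estimate, whether or not rescue was given. This includes mITT patients who attend the 3-month visit with an open wound. Closure reported by week 12 counts at the reported week. Patients who stop answering without a Yes, and with no record of an open wound at or after week 12, are missing and counted by arm.

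Also report by arm, without a test, the number of wounds open at week 12 and the number of patients rescued.

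The cost is a few lines of text. No new visits, patients or data are needed: the week-12 answers and later visits are already planned, and for rescue "The date and time of rescue medication administration as well as the name and regimen of the rescue medication will be recorded in RedCAP". The downside is that the Hodges-Lehmann estimate depends slightly on the code (7 v 9 case: −1.81 weeks coded 13, −1.96 coded 18), as do the mean and SD. The test does not, since the rank stays the same. If almost all wounds close by week 12, the rule changes little.
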